5.1 Induction 1 – ADE (10+3+5) with GO

The following therapy guidelines are for patients during Induction I. Patients on Induction I will receive gemtuzumab in addition to ADE therapy based on GO genotyping. Induction I lasts a total of 28 days.

Intrathecal Cytarabine: IT

Given at time of diagnostic lumbar puncture or Day 1.

Age-based dosing:

Age (yrs)	Dose
0-0.99	20 mg
1-1.99	30 mg
2-2.99	50 mg
≥ 3	70 mg

For CNS positive patients: add twice weekly IT AraC doses until CNS is clear, plus two additional treatments. A minimum of four intrathecal treatments are to be administered during the period of three weeks following diagnosis.

Cytarabine: Slow IV Push (e.g., over 1-2 minutes)

100 mg/m²/dose (3.3 mg/kg/dose if BSA < 0.6 m²) every 12 hours (total of 20 doses) on Days 1-10.

Daunorubicin (DAUN): IV over 15 minutes

50 mg/m²/dose (1.67 mg/kg/dose if BSA < 0.6 m²) every other day (total of 3 doses) on Days 1, 3, 5.

See Section 6 if direct bilirubin is > 2.

Etoposide (ETOP): IV over 60 – 120 minutes

100 mg/m²/dose (3.3 mg/kg/dose if BSA < 0.6 m²) daily (total of 5 doses) on Days 1-5.

See Section 6 if direct bilirubin is > 2.

Gemtuzumab Ozogamicin (GO): IV over 2 hours

3 mg/m²/dose (0.1 mg/kg/dose if BSA < 0.6 m²) once (total of 1 dose) on Day 6 through 10.

GO to be given once when GO genotyping demonstrates CC genotype. It can be given on any day between days 6-10 of Induction 1.

Pre-medicate with an antihistamine such as diphenhydramine, 1 mg/kg IV (max 50 mg), acetaminophen 10-15 mg/kg PO (max 650 mg) and methylprednisolone (1mg/kg) PO/IV. Repeat every 4 hours as needed to prevent post infusion complications.

Following Induction I, the next course (Induction II) starts on Day 29 or when blood count parameters and clinical condition are acceptable (whichever occurs later). This should not precede the end of course marrow exam.

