10.1 CRITERIA FOR REMOVAL FROM PROTOCOL THERAPY AND OFF STUDY CRITERIA

10.2 Criteria for Removal from Protocol Therapy

1. Failure to attain or maintain remission following Induction II ($\geq 5\%$ malignant blasts or extramedullary disease).
2. Relapse after Induction II of any site following remission.
3. Refractory CNS leukemia following 6 doses of IT cytarabine therapy in Induction I or Induction II.
4. CNS leukemia at start of Induction II after treatment for CNS leukemia in Induction I.
5. Grade 3 or greater neurotoxicity from HD cytarabine or,

6. Other intolerable or unacceptable toxicity secondary to the standard chemotherapy backbone.
7. Refusal of further protocol therapy by patient/parent/guardian.
8. Completion of planned therapy.
9. Physician determines it is in patient's best interest.
10. Development of a second malignancy.
11. Graft failure

Patients who are off protocol therapy are to be followed until they meet the criteria for Off Study (see below). Follow-up data will be required unless consent was withdrawn.

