10.3 Off Study Criteria

1. Death.
2. Lost to follow-up.
3. Patient enrollment onto another study with tumor therapeutic intent (e.g., at recurrence).*
4. Withdrawal of consent for any further data submission.
5. Tenth anniversary of study entry.
6. Excluded constitutional condition or oncologic diagnosis is indicated following enrollment
7. FLT3/ITD status is unknown at End of Induction I.

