11.1 STATISTICAL CONSIDERATIONS

Sample size: This is a pilot study aimed at utilizing a risk-stratified approach along with pharmacogenomics to treat newly diagnosed patients with AML. Annually we expect to have 10-20 de novo AML patients to be diagnosed and treated at our institution. This two-year study would be expected to enroll approximately 30 patients (both low and high risk) during that time period. As a pilot study, this trial is not hypothesis-driven but rather estimation-driven, and the sample size is based on a feasible two-year target for our institution.

Descriptive statistics will be conducted for demographic and patient characteristic variables, including toxicity related variables. Mean and standard deviation will be used for continuous variables and frequency and percent will be used for categorical variables.

Primary Endpoints:

1. Event-free survival: Event-free survival (EFS) is defined as the time from on study to death, failure to achieve remission or relapse, where those patients who do not experience these events will be censored at last follow-up date. EFS will be estimated using the Kaplan-Meier method for newly diagnosed patients with pediatric acute myeloid leukemia using a risk stratified approach.

Secondary Endpoints:

1. Disease-free survival: Disease-free survival (DFS) from end of first course of therapy is defined as time from end of first course of therapy to death or relapse, where those patients who do not experience these events will be censored at last follow-up date. DFS will be estimated using the Kaplan-Meier method for newly diagnosed patients with pediatric acute myeloid leukemia using a risk stratified approach.
2. Overall survival: Overall survival (OS) is defined as (1) time from study entry and (2) from end of first course of therapy to death, where those who do not die will be censored at

last follow-up date. OS will be estimated using the Kaplan-Meier method for newly diagnosed patients with pediatric acute myeloid leukemia using a risk stratified approach.

3. Minimal residual disease: Minimal residual disease (MRD) is the proportion of patients that are in remission (MRD negative) after one cycle of induction chemotherapy in both the GO and non-GO groups. Descriptive statistics (frequency and percent) will be used to estimate the frequency of MRD.

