4. Disease-free-survival MRD negative: Disease-free-survival, defined as time from end of first course of therapy to death or relapse, will be estimated for MRD negative patients who lack high or low risk molecular and cytogenetic features using the Kaplan-Meier method.
5. Cardiac ejection fraction: Descriptive statistics (frequency and percent) will be used to estimate the frequency of patients that develop cardiac ejection fraction <50% (CTCAE V5.0 grade 2 or greater dysfunction) either during therapy (early cardiotoxicity) or after completion of therapy (late cardiotoxicity).

Exploratory Endpoints:

1. Molecular abnormalities: Descriptive statistics will be used to describe the molecular abnormalities seen in de-novo AML samples using comprehensive genomic testing.

Analysis Datasets:

All eligible patients who receive at least one dose of protocol therapy will be included in the primary efficacy analysis. Safety analysis will be conducted using the Safety Population, defined as any participant receiving at least one dose of study treatment.

Interim Analysis:

The rates of infectious and hematologic toxicities with each chemotherapy course are well established from prior COG study AAML0531 (refer to table below). These toxicity rates will be monitored after enrollment of the first 10 patients and subsequently after the next 10 patients are enrolled. While this is highly unlikely to happen, if toxicity rates are exceeding those expected for each course, the study will be stopped.

AAML0531	ADE	ADE +GO	MA	AE	Capizzi
Infection incidence					
Documented infection	35 %	36 %	69%	49 %	67%
Neutropenic fever	31 %	32 %	23%	23 %	18%
Hematologic Recovery (days)					
Median time to platelets >50K	26	28	38	25	42
Median time to ANC >500	30	30	37	27	40

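### Section 10.3 item 7 ends follow-up at about day 28 for eligible, treated patients with unknown FLT3/ITD status, so EFS and OS censor them early

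*Combined protocol and SAP*

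**What the plan says.** Four statements in the combined protocol and SAP bear on this.

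- Section 10.3 (Off Study Criteria), item 7: "FLT3/ITD status is unknown at End of Induction I". The same list contains the planned end of follow-up, "Tenth anniversary of study entry".
- Section 10.2 (Criteria for Removal from Protocol Therapy): "Patients who are off protocol therapy are to be followed until they meet the criteria for Off Study". Unknown FLT3/ITD status is not one of the eleven reasons listed there for stopping protocol therapy.
- Section 11.1, primary endpoint: "Event-free survival (EFS) is defined as the time from on study to death, failure to achieve remission or relapse". For anyone without such an event, the plan then gives its censoring rule: "where those patients who do not experience these events will be censored at last follow-up date". OS and DFS use the same censoring rule.
- Section 11.1, Analysis Datasets: "All eligible patients who receive at least one dose of protocol therapy will be included in the primary efficacy analysis". FLT3 status is mentioned neither there nor in the eligibility criteria (3.1, 3.2).

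On timing, section 5.1 says "Induction I lasts a total of 28 days".

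**The concern.** Most other off-study items describe patients who have died, cannot be reached, have withdrawn consent, have joined another treatment study or have reached ten years. Item 6 covers a patient found to have an excluded condition. Item 7 is different: the patient is eligible, has been treated, still consents and can be contacted. Only a test result is missing. By contrast, a patient who refuses further therapy or has graft failure stays in follow-up under 10.2.

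This is an estimation-only pilot of about 30 patients, so the EFS estimate is its main product. Kaplan-Meier assumes that censored patients have the same later prognosis as those still followed. FLT3 status enters the risk classification in section 4.0, so a missing result could be related to prognosis, and that assumption would then be doubtful. OS is affected in the same way. DFS and the second OS definition start at the end of the first course, so an affected patient contributes almost no time to either. Late cardiotoxicity, a secondary endpoint, is not observed at all in these patients, although they have received an anthracycline course.

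**Working it through.** **Reading the sections together.** Item 7 is an off-study criterion (10.3). Follow-up runs only to the off-study point (10.2). That point falls at the end of a 28-day course (5.1). An event-free patient is censored at last follow-up (11.1) and remains in the primary set (11.1). The result is censoring at about day 28. Section 10.2 places failure to attain remission after Induction II, which is later than this, so that event could not be recorded either.

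**The plan's own figure.** Section 11.1 expects 10–20 patients a year for two years: 2 × 10 = 20 to 2 × 20 = 40, midpoint 30. The planned 30 reproduces. No alpha, power or target EFS is stated.

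**Follow-up lost.** Three years is the horizon used in the background section. 28 / 1,095.75 days = 2.6% of it.

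**How many patients (assumed; no rate is given).** If a share *u* of 30 patients has unknown status, the expected number is 30*u* and the chance of at least one is 1 − (1 − *u*)^30.

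- *u* = 2%: 0.6 expected, 45.5% chance of at least one
- *u* = 5%: 1.5 expected, 78.5%
- *u* = 10%: 3.0 expected, 95.8%

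**Shift in EFS.** Take a full-cohort EFS of 15/30 = 50%, in line with the roughly 50% given in the introductory summary. Let *k* patients be censored at day 28, with everyone else followed to the horizon and no event before day 28. The estimate then rests on 30 − *k* patients. The half-width is 1.96 × √(0.5 × 0.5 / (30 − *k*)).

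| *k* | All lost would have failed | All lost would be event-free | Largest shift | 95% half-width |
|---|---|---|---|---|
| 0 | 50.0% | 50.0% | 0 | 17.9 |
| 1 | 15/29 = 51.7% | 14/29 = 48.3% | 1.7 | 18.2 |
| 2 | 15/28 = 53.6% | 13/28 = 46.4% | 3.6 | 18.5 |
| 3 | 15/27 = 55.6% | 12/27 = 44.4% | 5.6 | 18.9 |

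These ratios approximate Kaplan-Meier. If two of the 15 events fell before day 28, the *k* = 3 extremes would be (28/30) × (15/25) = 56.0% and (28/30) × (12/25) = 44.8%.

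**The same question from the reported estimate.** Suppose Kaplan-Meier gives 50% and *k* = 3. The full-cohort value lies between (27 × 0.5 + 0)/30 = 45.0% and (27 × 0.5 + 3)/30 = 55.0%. As a pessimistic illustration, give the lost patients the 16% progression-free survival that section 2.4 quotes for high allelic ratio. Then (27 × 0.5 + 3 × 0.16)/30 = 46.6%, an overstatement of 3.4 points. For *k* = 1, (29 × 0.5 + 0.16)/30 = 48.9%, an overstatement of 1.1 points.

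**The case against.** The strongest reply is that item 7 will hardly ever apply. FLT3 testing on marrow is a baseline study (8.1). Sorafenib starts on Day 11 of Induction I for FLT3-ITD patients (5.2), so the plan expects the result well before day 28. This is a single centre, and all patients also have a genomic panel sent (2.5), although its turnaround of up to four weeks makes it a late backup. All of this stands, and it is why the number affected is treated as small. At zero patients the effect is nil, and even at three the shift is well inside the sampling error.

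A second reply is that section 10.2 ends by requiring follow-up data from everyone who has not withdrawn consent. That sentence concerns patients off protocol therapy and comes directly after follow-up has been limited to the off-study point. It makes the text less clear but does not plainly override 10.3.

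A third reply is that item 7 works like item 6, as a late eligibility check. The documents do not say so: FLT3 status is not an eligibility criterion, so the analysis-set rule retains these patients.

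A reader might also infer that the missing results would belong to sicker patients and so inflate EFS. The documents do not establish this. Section 3.1 admits patients for whom marrow is clinically prohibitive, and those with isolated myeloid sarcoma, and names no alternative FLT3 specimen. That makes a missing result possible. But the blood substitution requires adequate flow cytometry and cytogenetics/FISH, and nothing shows that FLT3 would be unknown in these patients or that they would do worse.

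**Conclusion.** The point holds as a minor one. A stated rule, rather than a missing detail, ends outcome observation at about day 28 for eligible, treated patients whose FLT3/ITD status is unknown.

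A reader might conclude that these patients are removed from the primary EFS. They are not: they stay in the analysis set, and a death during Induction I counts as an event. What is lost is everything after that.

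The shift of about 1.7 points for one patient and 5.6 points for three rests on an assumed 0–3 affected patients, an EFS near 50%, no event before day 28, and the all-fail or all-event-free extremes. The direction is unknown. With no decision threshold on EFS and a half-width of about 18 points, no conclusion of the trial turns on it. It still merits correction because the censoring is avoidable and could be informative.

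**What to change.** Remove item 7 of section 10.3 as a reason to end follow-up. State in sections 10 and 11.1 that patients with unknown FLT3/ITD status at the end of Induction I remain in event, survival and late-cardiotoxicity follow-up, and in the EFS and OS analyses, whatever their protocol-therapy status. For any who nevertheless are not followed, add a sensitivity analysis that counts them first all as failures and then all as event-free.

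Moving the item into section 10.2 is not proposed, because that would write in a rule for stopping treatment. Whether these patients continue protocol therapy is a clinical matter for the sponsor, who should reconcile 10.2 and 10.3 on it. The statistical change does not depend on the answer.

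The cost is a small text amendment and continued follow-up of perhaps 0–3 patients at the same centre.

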11.1 STATISTICAL CONSIDERATIONS

Sample size: This is a pilot study aimed at utilizing a risk-stratified approach along with pharmacogenomics to treat newly diagnosed patients with AML. Annually we expect to have 10-20 de novo AML patients to be diagnosed and treated at our institution. This two-year study would be expected to enroll approximately 30 patients (both low and high risk) during that time period. As a pilot study, this trial is not hypothesis-driven but rather estimation-driven, and the sample size is based on a feasible two-year target for our institution.

Descriptive statistics will be conducted for demographic and patient characteristic variables, including toxicity related variables. Mean and standard deviation will be used for continuous variables and frequency and percent will be used for categorical variables.

Primary Endpoints:

1. Event-free survival: Event-free survival (EFS) is defined as the time from on study to death, failure to achieve remission or relapse, where those patients who do not experience these events will be censored at last follow-up date. EFS will be estimated using the Kaplan-Meier method for newly diagnosed patients with pediatric acute myeloid leukemia using a risk stratified approach.

Secondary Endpoints:

1. Disease-free survival: Disease-free survival (DFS) from end of first course of therapy is defined as time from end of first course of therapy to death or relapse, where those patients who do not experience these events will be censored at last follow-up date. DFS will be estimated using the Kaplan-Meier method for newly diagnosed patients with pediatric acute myeloid leukemia using a risk stratified approach.
2. Overall survival: Overall survival (OS) is defined as (1) time from study entry and (2) from end of first course of therapy to death, where those who do not die will be censored at

last follow-up date. OS will be estimated using the Kaplan-Meier method for newly diagnosed patients with pediatric acute myeloid leukemia using a risk stratified approach.

3. Minimal residual disease: Minimal residual disease (MRD) is the proportion of patients that are in remission (MRD negative) after one cycle of induction chemotherapy in both the GO and non-GO groups. Descriptive statistics (frequency and percent) will be used to estimate the frequency of MRD.
4. Disease-free-survival MRD negative: Disease-free-survival, defined as time from end of first course of therapy to death or relapse, will be estimated for MRD negative patients who lack high or low risk molecular and cytogenetic features using the Kaplan-Meier method.
5. Cardiac ejection fraction: Descriptive statistics (frequency and percent) will be used to estimate the frequency of patients that develop cardiac ejection fraction <50% (CTCAE V5.0 grade 2 or greater dysfunction) either during therapy (early cardiotoxicity) or after completion of therapy (late cardiotoxicity).

Exploratory Endpoints:

1. Molecular abnormalities: Descriptive statistics will be used to describe the molecular abnormalities seen in de-novo AML samples using comprehensive genomic testing.

Analysis Datasets:

All eligible patients who receive at least one dose of protocol therapy will be included in the primary efficacy analysis. Safety analysis will be conducted using the Safety Population, defined as any participant receiving at least one dose of study treatment.

Interim Analysis:

The rates of infectious and hematologic toxicities with each chemotherapy course are well established from prior COG study AAML0531 (refer to table below). These toxicity rates will be monitored after enrollment of the first 10 patients and subsequently after the next 10 patients are enrolled. While this is highly unlikely to happen, if toxicity rates are exceeding those expected for each course, the study will be stopped.

AAML0531	ADE	ADE +GO	MA	AE	Capizzi
Infection incidence					
Documented infection	35 %	36 %	69%	49 %	67%
Neutropenic fever	31 %	32 %	23%	23 %	18%
Hematologic Recovery (days)					
Median time to platelets >50K	26	28	38	25	42
Median time to ANC >500	30	30	37	27	40

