2.3 Rationale for use of Dexrazoxane with anthracyclines

Cumulative incidence of heart failure and other cardiac events in patients with acute leukemias ranges from 4-10% at 10-20 years from diagnosis^{28,29}. While late cardiotoxicity has been

described well following anthracycline exposure above 250-300 mg/m² doxorubicin equivalents, early cardiotoxicity is a growing concern³⁰. Evaluation of cardiotoxicity (defined as grade 2 or higher left ventricular dysfunction per CTCAE version 5.0) on COG AAML0531 showed an incidence of 12% over a five-year follow-up period with most of the events occurring while on protocol therapy. Black, older patients (>1 year age) and concurrent infection were risk factors associated with worse cardiac outcomes³⁰.

Dexrazoxane is a bis-dioxopiperazine compound that was introduced in the early 1990's and has been shown to reduce cardiotoxicity related to anthracyclines initially in animal models and later in clinical studies^{31,32}. While the exact mechanism is poorly understood, it is believed that anthracyclines form complexes with heavy metals specifically iron and generate free radicals that cause cardiac damage³³. Dexrazoxane binds to iron and prevents the generation of free radicals thereby reducing cardiotoxicity. Dexrazoxane has been used successfully in combination with various chemotherapy regimens with acceptable toxicity and enhanced cardio-protection^{34,35}. While there was concern regarding development of secondary malignancies with exposure to dexrazoxane, recent literature has not supported this side-effect³⁶. In this study, all patients will receive dexrazoxane in anthracycline-containing treatment courses. We will closely monitor for infection, cardiac, hepatic and hematologic toxicities as well as development of secondary malignancies. In addition, we will obtain more precise measurements of cardiac function using echocardiogram at the end of each course (Section 8.0) as noted in Table 4.

Table 4: Variables of cardiac function to be determined using echocardiography

Left ventricle (LV) remodeling	LV thickness to dimension ratio
LV myocardial deformation	Strain and Strain rate imaging
LV systolic function	LV Ejection Fraction using biplane Simpson method LV Shortening fraction using 2D and M-mode Mitral and septal S'

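### Late cardiotoxicity is planned as a crude percent with no time horizon, so its value depends on the data cut and on attrition: a minor, cheaply fixed weakness of interpretation

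*Combined protocol and SAP*

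**What the plan says.** Section 11.1 (Secondary Endpoints, item 5) says: "Descriptive statistics (frequency and percent) will be used to estimate the frequency of patients that develop cardiac ejection fraction <50" percent. It splits the endpoint into early (during therapy) and late (after therapy is complete). The endpoint list that follows Section 1.3 calls it a proportion, and Objective 4 in Section 1.2 asks for incidence in patients who receive the four-cycle regimen. None of these gives a time point, an analysis date, a censoring rule or a rule for deaths.

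Follow-up will be unequal. On accrual, Section 11.1 states: "This two-year study would be expected to enroll approximately 30 patients (both low and high risk) during that time period". Under Section 10.3 a patient leaves at death, loss to follow-up, withdrawal of consent or entry to another therapeutic study, and at the latest at the "Tenth anniversary of study entry". That last rule caps follow-up but sets no analysis time.

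For EFS and DFS the same section uses Kaplan-Meier, "where those patients who do not experience these events will be censored at last follow-up date", and it treats OS likewise.

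Section 6.3.1 requires an echocardiogram during follow-up without saying when. The schedule in Section 8.1 has columns for baseline, each course, end of therapy and relapse or refractory disease, but none for off-therapy follow-up.

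**The concern.** A cumulative count of late events can only rise as patients are watched for longer, and patients who leave early have less time in which an event could be seen. A percent without a horizon mixes the risk with the length of observation. Two reports on the same patients, cut at different dates, would print different figures, and neither would say to what time it refers.

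Reducing cardiotoxicity is a stated aim of the regimen, so readers will look at this number. An early report could well show zero late events, and a bare 0% with no interval or horizon could be taken to mean absence of risk.

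**Working it through.** **The plan's own figure.** Accrual of 10 to 20 a year for two years gives 20 to 40 patients, midpoint 30, which is the stated target. The plan gives no figure or precision for late cardiotoxicity, so what follows is an illustration.

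**Inputs.** From the documents: n = 30; two-year accrual; OS of 65% (lower end of the three-year range in Section 2.1); EFS of about 50% (opening summary); 12% cardiotoxicity over five years, mostly on therapy (Section 2.3). Assumed: uniform entry; therapy lasting w = 0.5 years; the EFS figure read as three-year; half of non-death EFS events leaving for another study; constant late hazard h of 0.0085 or 0.0156 a year, chosen to give about 3.0% or 5.4% at five years from end of therapy (25% or 45% of the 12%).

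- Death hazard d = -ln(0.65)/3 = 0.1436.
- Other-exit hazard x = 0.5 × (-ln(0.50)/3 - 0.1436) = 0.5 × (0.2310 - 0.1436) = 0.0437.
- Still followed at end of therapy: exp(-(d + x) × 0.5) = 0.911.

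**Crude late percent at a cut T years after last enrolment.** With k = h + d + x, and m the mean of exp(-kt) for t uniform between T - 0.5 and T + 1.5, crude = 0.911 × (h/k) × (1 - m). Example for h = 0.0085, T = 1: k = 0.1958, m = 0.750, crude = 0.911 × 0.0434 × 0.250 = 0.99%.

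| Cut after last enrolment | h = 0.0085: percent (events; SD) | h = 0.0156: percent (events; SD) |
|---|---|---|
| 1 year | 0.99 (0.3; 1.8) | 1.80 (0.5; 2.4) |
| 4 years | 2.30 (0.7; 2.7) | 4.17 (1.3; 3.7) |
| 8 years | 3.20 (1.0; 3.2) | 5.74 (1.7; 4.3) |

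Events are 30 × crude; SD = sqrt(p(1 - p)/30), in percentage points. The shift from the 1-year cut is 1.3 to 2.4 points at 4 years and 2.2 to 3.9 at 8 years, in each case less than the SD at the later cut. The chance of no late event, (1 - p)^30, is 58 to 74% at the 1-year cut and 17 to 38% at the 8-year cut.

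**Shape of the hazard.** The 4-year to 1-year ratio is 2.3 here. With a Weibull late hazard of shape 0.5 (falling) it is about 1.5, and with shape 1.5 (rising) about 3.6. The direction does not change.

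**Attrition.** With other assumptions (10% late risk at ten years, therapy 0.4 years), the crude percent at the 8-year cut is 8.7% if nobody leaves, 4.7% with 65% retained at three years and 3.5% with 50% retained.

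**Fixed-time cumulative incidence.** With death competing and other exits censored, CIF(t) = h/(h + d) × (1 - exp(-(h + d)t)). At 1, 3 and 5 years from end of therapy this is 0.8, 2.0 and 3.0%, or 1.4, 3.7 and 5.4%. It does not depend on the cut, provided follow-up reaches t and events are seen when they occur.

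**Two conditions on that estimator.**

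- *Deaths.* If everyone is censored at the last echocardiogram, each death is censored before it can compete, and the estimate becomes 1 - exp(-5h) = 4.2% or 7.5% at five years instead of 3.0% or 5.4%.
- *Detection.* An event is seen only at an echocardiogram. With one every s years, the detected incidence by t is the sum over visits q = s, 2s, ... up to t of exp(-dq) × (exp(-h(q - s)) - exp(-hq)). At five years this is 2.8% or 5.0% with annual visits and 2.2% or 4.0% with two-yearly visits; at one year the two-yearly schedule gives 0%.

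**Precision at zero events.** The exact 95% upper limit is 11.6% for 0/30. A late risk set of 30 × 0.931 alive at 0.5 years × (1 - 0.066 to 0.090 early events) is about 25 to 26 patients, with upper limit 13.2 to 13.7%.

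**The case against.** The trial is declared to be estimation-driven, frequency and percent is its convention for toxicity variables, and no test or stopping rule uses this endpoint. With 0.3 to 1.7 expected events, either method will often give a nearly uninformative number with a wide interval, and an event count with median echocardiographic follow-up would meet much of the concern. All of that stands and limits the point to a minor one. It does not remove it: a percent without a horizon remains undefined however few the events.

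A reader might infer that the missing horizon is what stops the result being set against the rates in Section 2.3. The documents do not support this. The plan makes no such comparison; those rates are background to the use of dexrazoxane. The AAML0531 evaluation "showed an incidence of 12% over a five-year follow-up period with most of the events occurring while on protocol therapy", so it combines early and late events. The other rate reads: "Cumulative incidence of heart failure and other cardiac events in patients with acute leukemias ranges from 4-10% at 10-20 years from diagnosis". That is a different event with a different time origin, at or beyond the ten-year limit on follow-up here. A late-only estimate would match neither, even with a horizon.

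A reader might also infer that the planned analysis is biased or conceals toxicity. Nothing in the documents shows that.

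The early/late boundary is unclear for transplanted patients. Section 2.1 places transplant after two or three courses, while Section 10.2 lists "Graft failure" as a reason for removal from protocol therapy, so the end of therapy could fall before or after transplant. This mainly concerns patients outside Objective 4 as worded, and is secondary.

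**Conclusion.** The point holds as a minor weakness of interpretation in one component of a secondary endpoint. In the main illustration the expected percent roughly doubles between cuts 1 and 4 years after last enrolment (2.3 times) and roughly triples by 8 years (3.2 times), while the underlying risk is unchanged. The early component is largely unaffected.

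The direction follows from the documents alone: a crude percent, no horizon and unequal follow-up. The size does not. It rests on the assumed late hazard, length of therapy, accrual pattern and exit rates, none of which the plan gives. Fixed estimation times cure the problem only if the follow-up echocardiograms are scheduled to match them, so the gap between Sections 6.3.1 and 8.1 is part of the same point.

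**What to change.** In Section 11.1:

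- Keep the early percent and add an exact 95% confidence interval.
- Report late cardiotoxicity as Aalen-Johansen cumulative incidence of first EF below 50% at prespecified times from end of protocol therapy, with 95% confidence intervals.
- Count a death on study as a competing event at its date, even if the last echocardiogram was earlier. Censor patients who are alive at their last echocardiogram before the data cut, or before leaving the study for a reason other than death.
- Report the event count, number at risk and median echocardiographic follow-up.
- Give the result for four-cycle patients, the population of Objective 4, alongside the Safety Population.
- State the start point for transplanted patients and use it for the early/late boundary too.

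Reconcile Section 6.3.1 with the schedule in Section 8.1 so that follow-up echocardiograms have stated times, and set the estimation times to coincide with them.

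The cost is analysis text, one definition and dates for an examination the protocol already requires; no extra patients. Dated echocardiograms are, however, a commitment over several years, and intervals stay wide. Censoring at the last echocardiogram assumes that patients without later ones resemble those who have them. Later time points need a later report: if therapy lasts about 0.5 years, all patients can have reached 1, 3 or 5 years from end of therapy only 1.5, 3.5 or 5.5 years after last enrolment.
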